## Chapter 5: Natural History Study Follow-up Visits

753

### 754 5.1 Follow-up Schedule

755 Follow-up Visits or phone calls will occur annually. Participants in the Younger Age Cohort  
 756 (YAC) and Vision Cohorts 1 and 2 will have annual in-person follow-up visits for four years  
 757 after the Baseline Visit. Participants in Vision Cohort 3 will receive annual follow-up phone calls  
 758 for three years after the Baseline Visit and will only return to the site for the last study visit (48-  
 759 Month Visit).

760 The Baseline Visit date is considered study day zero (0) from which follow-up windows are  
 761 timed. The Follow-up Visit date will be the date the Follow-up Visit testing procedures started.  
 762 All Follow-up Visit testing procedures will be completed on the same date, other than the PROs  
 763 as noted in Section 5.3 Follow-up Procedures.

### 764 5.2 Target Timelines

765 Target dates and windows for each study Follow-up Visit for all cohorts are shown below. Dates  
 766 and windows are timed from Baseline Visit date.

### 767 Schedule for Follow-up Visits or Phone Calls

VISIT SCHEDULE	VISIT TYPE	TARGET DATE*	TARGET WINDOW*	ALLOWABLE WINDOW*
12-Month	YAC + Vision Cohort 1 & 2: In-person Visit	52 Weeks	± 4 Weeks	± 6 Weeks
	Vision Cohort 3: Phone Call			
24-Month	YAC + Vision Cohort 1 & 2: In-person Visit	104 Weeks	± 4 Weeks	± 6 Weeks
	Vision Cohort 3: Phone Call			
36-Month	YAC + Vision Cohort 1 & 2: In-person Visit	156 Weeks	± 4 Weeks	± 6 Weeks
	Vision Cohort 3: Phone Call			
48-Month	All Cohorts In-person Visit	208 Weeks	± 4 Weeks	± 6 Weeks

768 \*Timed from Baseline Visit Date

769 The goal is for all participants to complete all scheduled study visits. However, participants who  
 770 (because of unforeseen circumstances) are unable or unwilling to return for all follow-up visits  
 771 will be permitted to return for key visits only as an alternative to withdrawal from the study.  
 772 Additional office visits may occur as needed.

773 **5.3 Follow-up Visit Testing Procedures**

774 The following procedures will be performed at the Follow-Up Visits, unless otherwise specified.  
 775 An overview of the equipment and certification requirements for all testing is in section 6.1. All  
 776 ocular testing will be performed in each eye, OD first and then OS. Follow-up Visit procedures  
 777 will last approximately three (3) hours. The testing procedures are detailed in the **Uni-Rare**  
 778 **Clinical Site Manual of Procedures.**

779 **5.3.1 Younger Age Cohort**

- 780 1. Medical updates to include:
- 781 ♦ New or changed adverse events (AEs)
  - 782 ♦ New ocular procedures
  - 783 ♦ New or changed medications
- 784 2. Patient Reported Outcomes (PROs)
- 785 ♦ ViSIO-ObsRO
  - 786 ♦ The PROs may be completed in person or remotely (phone or other remote  
 787 methods) any time within the Allowable Window of the associated visit (not  
 788 required to be the same day as the rest of the Follow-up Visit).
- 789 3. Complete ophthalmic examination to include:
- 790 ♦ Slit lamp biomicroscopy
  - 791 ♦ Indirect ophthalmoscopy
- 792 4. Visual Acuity (including refraction, HOTV, BRVT if needed, LLVA if needed)
- 793 ♦ The visual acuity (VA) Snellen score will determine whether LLVA or BRVT  
 794 will be performed. The criteria are defined in the **Uni-Rare Clinical Site Manual**  
 795 **of Procedures.**
- 796 5. Intraocular Pressure (IOP)
- 797 ♦ IOP measurements are to be taken prior to pupil dilation.
- 798 6. Color Vision
- 799 ♦ Desaturated (Lanthony D15)
- 800 7. Spectral Domain Optical Coherence Tomography (SD-OCT)
- 801 ♦ Volume Scan
  - 802 ♦ Vertical and Horizontal Scan
  - 803 ♦ If unable to perform OCT testing on the Heidelberg Spectralis, a site may use the  
 804 handheld Bioptogen/Envisu to perform OCT testing for qualitative purposes **with**  
 805 **approval from the Coordinating Center.**
- 806 8. Axial Length and Corneal Curvature Measurements
- 807 9. Optos Fundus Autofluorescence (FAF)\*

- 808 10. Full-field Electroretinogram (ffERG)\*  
 809     ◆ Complete at 48-Month Follow-up Visit Only  
 810 11. Full-field Stimulus Threshold (FST)\*

811 **5.3.1.1 Age-Up Procedures**

812 Participants in the Younger Age Cohort who turn 8 years old (age-up) during the NHS study  
 813 period should attempt to have static perimetry, microperimetry, and contrast sensitivity  
 814 testing performed at the next study visit after they turn 8 years old and at every subsequent  
 815 visit, until the end of the study period.

- 816 12. Static Perimetry (SP)  
 817 13. Fundus Guided Microperimetry (MP)\*  
 818 14. Contrast Sensitivity

819 **Note:** All testing procedures are to be *attempted* for participants in the Younger Age Cohort.  
 820 If a child is unwilling to or unable to complete an examination, the procedure is to be  
 821 skipped.

822 *\*If a site does not have the required equipment, participation in this test may be waived with*  
 823 *approval from the Coordinating Center.*

824 **5.3.2 Vision Cohorts 1 & 2**

- 825 1. Medical updates to include:  
 826     ◆ New or changed adverse events (AEs)  
 827     ◆ New ocular procedures  
 828     ◆ New or changed medications  
 829 2. Patient Reported Outcomes (PROs)  
 830     ◆ Complete at 24-Month and 48-Month Follow-up Visits Only  
 831     ◆ **Adults (18+ years at Baseline):** PROMIS®-29, MRDQ, ViSIO-PRO  
 832     ◆ **Adolescents (12-17 years at Baseline):** LVP-FVQ II, ViSIO-PRO  
 833     ◆ **Children (8-11 years at Baseline):** LVP-FVQ II, ViSIO-ObsRO  
 834     ◆ The PROs may be completed in person or remotely (phone or other remote  
 835 methods) any time within the Allowable Window of the associated visit (not  
 836 required to be the same day as the rest of the Follow-up Visit).  
 837 3. Complete ophthalmic examination to include:  
 838     ◆ Slit lamp biomicroscopy  
 839     ◆ Indirect ophthalmoscopy  
 840 4. Visual Acuity (including refraction, ETDRS, BRVT if needed, LLVA if needed)

841                   ♦ The visual acuity (VA) letter score will determine whether LLVA or BRVT will  
 842 be performed. The criteria are defined in the **Uni-Rare Clinical Site Manual of**  
 843 **Procedures.**

844           5. Intraocular Pressure (IOP)

845                   ♦ IOP measurements are to be taken prior to pupil dilation.

846           6. Color Vision

847                   ♦ Desaturated (Lanthony D15)

848           7. Contrast Sensitivity

849           8. Spectral Domain Optical Coherence Tomography (SD-OCT)

850                   ♦ Volume Scan

851                   ♦ Vertical and Horizontal Scan

852           9. Axial Length and Corneal Curvature Measurements

853                   ♦ Only individuals who are under 18 years old at the Baseline Visit will continue to  
 854 have measurements taken at every annual visit until study completion.

855           10. Optos Fundus Autofluorescence (FAF)\*

856           11. Full-field Electroretinogram (ffERG)\*

857                   ♦ Complete at 48-Month Follow-up Visit Only

858           12. Full-field Stimulus Threshold (FST)\*

859           13. Static Perimetry (SP)

860           14. Fundus Guided Microperimetry (MP)\*

861           *\*If a site does not have the required equipment, participation in this test may be waived **with***  
 862 ***approval from the Coordinating Center.***

863           **5.3.3 Vision Cohort 3**

864           Phone contact will be scheduled at 12-, 24-, and 36-Month intervals. The purpose of the  
 865 phone contact will be to keep the participants engaged in the study during the interim  
 866 between the Baseline and 48-Month Follow-up Visits and to keep contact information  
 867 updated. Changes in medications and AEs will also be collected.

868           **The following will only be performed at 48-Month Visit:**

869                   1. Medical updates to include

870                           ♦ New or changed adverse events (AEs)

871                           ♦ New ocular procedures

872                           ♦ New or changed medications

873                   2. Patient Reported Outcomes (PROs)

874                           ♦ **Adults (18+ years at Baseline):** PROMIS®-29, MRDQ, ViSIO-PRO, ULV-  
 875 VFQ-50

- 876           ♦ **Adolescents (12-17 years at Baseline):** LVP-FVQ II, ViSIO-PRO
- 877           ♦ **Children (8-11 years at Baseline):** LVP-FVQ II, ViSIO-ObsRO
- 878           ♦ The PROs may be completed in person or remotely (phone or other remote
- 879           methods) any time within the Allowable Window of the associated visit (not
- 880           required to be the same day as the rest of the Follow-up Visit).
- 881        3. Complete ophthalmic examination to include:
- 882           ♦ Slit lamp biomicroscopy
- 883           ♦ Indirect ophthalmoscopy
- 884        4. Visual Acuity (including refraction, ETDRS, BRVT if needed, LLVA if needed)
- 885           ♦ The visual acuity (VA) letter score will determine whether LLVA or BRVT will
- 886           be performed. The criteria are defined in the **Uni-Rare Clinical Site Manual of**
- 887           **Procedures.**
- 888        5. Intraocular Pressure (IOP)
- 889           ♦ IOP measurements are to be taken prior to pupil dilation.
- 890        6. Spectral Domain Optical Coherence Tomography (SD-OCT)
- 891           ♦ Volume Scan
- 892           ♦ Vertical and Horizontal Scan
- 893        7. Axial Length and Corneal Curvature Measurements
- 894           ♦ Only individuals who were under 18 years old at the Baseline Visit will have
- 895           measurements taken at 48M visit.
- 896        8. Optos Fundus Autofluorescence (FAF)\*
- 897        9. Full-field Stimulus Threshold (FST)\*
- 898        *\*If a site does not have the required equipment, participation in this test may be waived **with***
- 899        ***approval from the Coordinating Center.***

900        **5.3.4 Unscheduled Visits**

901        Testing procedures at unscheduled visits are at the Investigator’s discretion. However, it is

902        recommended that procedures performed during these visits follow the standard protocol for

903        each procedure and be performed by certified personnel. Unscheduled visits will be recorded on

904        the FFB Consortium study website. Study images taken during unscheduled visits do not require

905        submission to the study website.

906

907

## Chapter 6: Testing Procedures and Questionnaires

### 908 6.1 Study Procedure Requirements

909 The study procedure instructions are detailed in the **Uni-Rare Clinical Site Manual of**  
 910 **Procedures**. An overview of the equipment and certification requirements for all testing are  
 911 provided in the table below.

Study Procedures	Description	Equipment Required (If applicable)	Site Personnel Delegation
Investigator taking overall responsibility for a visit	Oversees that consent process was performed in accordance with IRB/EC requirements; signs off on all eCRFs for a participant, eCRF edits, and protocol deviations.	N/A	Certified investigator
Coordinator taking responsibility for the visit	Oversees the data entry aspect of the visit; addresses protocol queries and signs off on deviations.	N/A	Certified coordinator
Informed Consent Form (ICF) Process	Explanation/review of study with the potential participant, including signature on the ICF.	N/A	Certified investigator or coordinator as permitted by the IRB/EC
Signature of Informed Consent Form	The participant and/or LAR sign the ICF. The person obtaining the ICF will also sign.	N/A	Certified investigator or coordinator as permitted by the IRB/EC
Data entry on study website	Data collected from the study participant will be directly entered on the FFB Study Website (strongly encouraged) or written on the paper CRF and transcribed on the FFB Study Website within seven (7) days.	Computer and internet connection	Certified coordinator or certified investigator with additional study website certification
Collect information regarding medical history, demographics, adverse events, medications	Sites will collect medical history, demographic information, Aes, and medications from the participant during each visit. This information can be confirmed by requesting medical records if needed.	N/A	Certified investigator or coordinator
Patient Reported Outcome (PRO)	There are six (6) questionnaires depending on age and Vision Cohort (details in section 6.2).	Study will provide	Certified investigator or coordinator
Ocular Exam	Including slit lamp biomicroscopy and indirect ophthalmoscopy	Any equipment is acceptable	Certified investigator
Intraocular Pressure (IOP)	Measurement of the fluid pressure inside the eye	Any equipment is acceptable	Clinical site personnel performing this test does not require a study specific certification. However, they must be trained and delegated by the PI per the SSDL.

Study Procedures	Description	Equipment Required (If applicable)	Site Personnel Delegation
Visual Acuity – Refraction	Refraction is done as a routine part of an eye exam to achieve best corrected visual acuity measures.	N/A	Clinical site personnel certified for refraction
Visual Acuity – ETDRS	Traditional measure of central visual function that represents foveal cone function.	EVA system or ETDRS charts	Clinical site personnel certified for VA (including ETDRS)
Visual Acuity – LLVA	Measures vision function in low luminance conditions	EVA system or ETDRS charts 2.0 neutral density filter to be provided by study	Clinical site personnel certified for VA (including LLVA)
Visual Acuity – BRVT	A three-level hierarchy for visual acuity testing better suited for low vision participants	BRVT charts provided by study	Clinical site personnel certified for BRVT
Visual Acuity – HOTV	Pediatric measure of central visual function that represents foveal cone function.	HOTV chart and lap card provided by study	Clinical site personnel certified for VA (including HOTV)
Color Vision	Measures the type and severity of color blindness	Lanthony D15 provided by study	Clinical site personnel performing this test does not require a study specific certification. However, they must be trained and delegated by the PI per the SSDL.
Contrast Sensitivity	Measure ability to distinguish between increments of light versus dark	CSV-1000E provided by study	Clinical site personnel performing this test does not require a study specific certification. However, they must be trained and delegated by the PI per the SSDL.
Spectral Domain Optical Coherence Tomography (SD-OCT) – Volume Scan	Scans provide objective, non-invasive measures of retinal structure	Heidelberg Spectralis**	Clinical site personnel certified for SD-OCT
Spectral Domain Optical Coherence Tomography (SD-OCT) – Vertical and Horizontal Scan	Scans provide objective, non-invasive measures of retinal structure	Heidelberg Spectralis**	Clinical site personnel certified for SD-OCT and vertical and horizontal scan
Axial Length and Corneal Curvature	Axial length measures the distance between the anterior and posterior poles of the eye. Corneal curvature determines the power of the cornea.	Any equipment is acceptable	Clinical site personnel performing this test does not require a study specific certification. However, they must be trained and delegated by the PI per the SSDL.

Study Procedures	Description	Equipment Required (If applicable)	Site Personnel Delegation
Optos Color Photos	Images provide objective, non-invasive visualization of the photoreceptor layer and RPE	Optos*	Clinical site personnel certified for Optos Color photos
Optos Fundus Autofluorescence (FAF)	Images provide objective, non-invasive map of lipofuscin in RPE	Optos*	Clinical site personnel certified for Optos FAF
Full-field Electroretinogram (ffERG)	Measures rod- and cone-mediated parts of the visual field	Diagnosys Espion*	Clinical site personnel certified for ffERG
Full-field Stimulus Threshold (FST)	Measures rod- and cone-mediated parts of the visual field	Diagnosys Espion*	Clinical site personnel performing this test does not require a study specific certification. However, they must be trained and delegated by the PI per the SSDL.
Static Perimetry (SP)	Measures sensitivity thresholds at specified test locations	Octopus 900 Pro (GATE Protocol)	Clinical site personnel certified for SP
Fundus guided microperimetry (MP)	Measures sensitivity thresholds at specified test locations	MAIA*	Clinical site personnel certified for MP
Kinetic Perimetry (KP)	Measures sensitivity thresholds at specified test locations	Any equipment is acceptable	(Historical) Does not need to be performed by study certified personnel or recorded in the SSDL

912 \*If site does not have required equipment, participation in this test may be waived **with**  
 913 **approval from the Coordinating Center**

914 \*\*If Younger Age Cohort participant is unable to perform OCT testing on the Heidelberg  
 915 Spectralis, a site may use the handheld Bioptogen/Envisu to perform OCT testing for qualitative  
 916 purposes **with approval from the Coordinating Center.**

917 **6.2 Questionnaires**

918 The following questionnaires will be administered in the study by a certified investigator or  
 919 coordinator. Each questionnaire takes about 15 minutes to administer.

Questionnaire	Type	Description	Vision Cohort	Age at Baseline
Michigan Retinal Degeneration Questionnaire (MRDQ)	Vision Function	The MRDQ is a psychometrically validated patient-reported outcome measure for inherited retinal degenerations questionnaire which consists of fifty-nine (59) questions measuring seven (7) unidimensional domains: central vision, color vision, contrast sensitivity, scotopic function, photopic peripheral vision, mesopic peripheral vision, and photosensitivity.	All	Adults ≥18 years

PROMIS-29® (Patient-Reported Outcomes Measurement Information System®)	Global Physical, Mental, and Social Health	The PROMIS®-29 contains items from seven PROMIS domains: depression; anxiety; physical function; pain interference; fatigue; sleep disturbance; and ability to participate in social roles and activities. The seven domains cover the most relevant areas of self-reported health for most people with chronic illness. There is also one 11-point rating scale for pain intensity.	All	Adults ≥18 years
Visual Symptom and Impact Outcomes Patient Reported Outcome (ViSIO-PRO)	Vision Function and HRQoL	The ViSIO-PRO instrument is designed to assess visual function symptoms, impacts on functional vision, and impacts on wider health-related quality of life (HRQoL). It has been designed for completion by adolescents (12-17) and adults (18+) with retinitis pigmentosa (RP).	All	Adolescents (12-17 years) & Adults (≥18 years)
Visual Symptom and Impact Outcomes Observer Reported Outcome (ViSIO-ObsRO)	Vision Function and HRQoL	The ViSIO-ObsRO instrument is designed to assess visual function symptoms, impacts on functional vision, and impacts on wider health-related quality of life (HRQoL). It has been designed for completion by parents/caregivers of children with retinitis pigmentosa (RP) aged 3-11 years.	All	Children 4-11 years
L. V. Prasad-Functional Vision Questionnaire (LVP-FVQ II)	Vision Function	The LVP-FVQ-II questionnaire consists of 23 questions. The questionnaire is used to assess self-reported difficulties in performing daily tasks in children with visual impairment.	All	Adolescents (12-17 years) & Children (8-11 years)
Ultra-Low Vision Visual Functioning Questionnaire (ULV-VFQ-50)	Vision Function	The ULV-VFQ-50 psychometrically evaluates a visual functioning questionnaire (VFQ) in an ultra-low vision (ULV) population	Vision Cohort 3	Adults ≥18 years

## Chapter 7: Unanticipated Problem and Adverse Event Reporting

921  
922  
923  
924  
925  
926  
927  
928  
929  
930  
931  
932  
933  
934  
935  
936  
937  
938  
939  
940  
941  
942  
943  
944  
945  
946  
947  
948  
949  
950  
951  
952  
953  
954  
955  
956  
957  
958

### 7.1 Unanticipated Problems

Site investigators will promptly report all unanticipated problems meeting the criteria below on an electronic case report form (eCRF). Sites overseen by the JCHR IRB must report Unanticipated Problems to the IRB within seven (7) calendar days of recognition. For this protocol, an unanticipated problem is an incident, experience, or outcome that meets all the following criteria:

- ◆ Unexpected (in terms of nature, severity, or frequency) given (a) the research procedures that are described in the protocol related documents, such as the IRB-approved research protocol and informed consent document; and (b) the characteristics of the subject population being studied.
- ◆ Related or possibly related to participation in the research (possibly related means there is a reasonable possibility that the incident, experience, or outcome may have been caused by the procedures involved in the research).
- ◆ Suggests that the research places participants or others at a greater risk of harm than was previously known or recognized (including physical, psychological, economic, or social harm).

The Coordinating Center also will report to the IRB all unanticipated problems not directly involving a specific site such as unanticipated problems that occur at the Coordinating Center or at another participating entity such as a laboratory.

These instances must be reported to the JCHR IRB within seven (7) calendar days of recognition. The Director of the Human Research Protection Program (HRPP) will report to the appropriate regulatory authorities if the IRB determines that the event indeed meets the criteria of an Unanticipated Problem that requires further reporting to fulfill the reporting obligations of the HRPP.

### 7.2 Adverse Events

**The following section on adverse events applies to the Natural History Study phase of the study.**

#### 7.2.1 Definitions

**Adverse Event (AE):** Any untoward medical occurrence (including laboratory findings) associated with study procedures whether the event is considered related.

**Serious Adverse Event (SAE):** Any untoward medical occurrence that results in any of the following outcomes:

- ◆ Death.
- ◆ A life-threatening adverse event: (a non-life-threatening event which, had it been more severe, might have become life-threatening, is not necessarily considered a serious adverse event).

- 959           ◆ Inpatient hospitalization or prolongation of existing hospitalization.
- 960           ◆ A persistent or significant disability/incapacity or substantial disruption of the ability
- 961           to conduct normal life functions.
- 962           ◆ A congenital anomaly or birth defect.

963 An important medical event that may not result in death, be life-threatening, or require  
964 hospitalization may be considered serious when, based upon appropriate medical judgment, they  
965 may jeopardize the patient or subject and may require medical and surgical intervention to  
966 prevent one of the outcomes listed in this definition.

967 **Note:** As this is a Natural History Study, the Investigator(s) will make the categorical  
968 determinations of Adverse Events, as described above, and will report each determination to the  
969 Coordinating Center, as per data collection.

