### 970           **7.2.2 Reportable Adverse Events**

971 For this protocol, a reportable adverse event includes all events meeting the definition of an  
972 adverse event.

973 All reportable Adverse Events whether volunteered by the participant, discovered by study  
974 personnel during questioning, or detected through ophthalmological examination, laboratory test,  
975 or other means will be reported on an adverse event form online.

976 The purpose of AE collection for the Uni-Rare study will be to provide historical controls for  
977 future clinical trials. As a no greater than minimal risk study, AEs do not require any specific  
978 reporting to regulatory or oversight bodies. However, each Principal Investigator (PI) is  
979 responsible for abiding by any other reporting requirements specific to their IRB or equivalent  
980 ethics oversight committee.

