#### 993           **No**

994 Evidence exists that the adverse event has an etiology other than the study procedure (for  
995 example, preexisting medical condition, underlying disease, intercurrent illness, or concomitant  
996 medication); and/or the adverse event has no plausible temporal relationship to study procedure.

997 **7.2.4 Severity (Intensity) of Adverse Event**

998 A severity assessment is a clinical determination of the intensity of an event. Thus, a severe  
 999 adverse event is not necessarily serious. For example, itching for several days may be rated as  
 1000 severe, but may not be clinically serious.

1001 The severity (intensity) of an adverse event will be rated on a three-point scale: (1) mild, (2)  
 1002 moderate, or (3) severe.

- 1003 **1. MILD:** Usually transient, requires no special treatment, and does not interfere with  
 1004 the participant’s daily activities.
- 1005 **2. MODERATE:** Usually causes a low level of inconvenience, discomfort or concern  
 1006 to the participant and may interfere with daily activities but is usually ameliorated by  
 1007 simple therapeutic measures and participant is able to continue in study.
- 1008 **3. SEVERE:** Interrupts a participant’s usual daily activities and causes severe  
 1009 discomfort.

1010 **7.2.5 Expectedness**

1011 As this is a Natural History Study, the expectedness for a serious adverse event will not be  
 1012 assessed.

1013 **7.2.6 Coding of Adverse Events**

1014 Adverse events will be coded using the Medical Dictionary for Regulatory Activities  
 1015 (MedDRA). To facilitate coding, the site will enter a preliminary MedDRA code

1016 **7.2.7 Outcome of Adverse Event**

1017 The outcome of each reportable adverse event will be classified by the Investigator(s) as follows:

- 1018 **1. RECOVERED/RESOLVED (COMPLETE RECOVERY)** – The participant  
 1019 recovered from the AE/SAE without sequelae. Record the AE/SAE stop date.
- 1020 **2. RECOVERED/RESOLVED WITH SEQUELAE** – AE/SAE where the subject  
 1021 recuperated but retained pathological conditions resulting from the prior disease or  
 1022 injury. Record the AE/SAE stop date.
- 1023 **3. FATAL** – A fatal outcome is defined as the SAE that resulted in death. Only the  
 1024 event that was the cause of death should be reported as fatal. AEs/SAEs that were  
 1025 ongoing at the time of death; however, were not the cause of death, will be recorded  
 1026 as “resolved” at the time of death.

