#### 8.1.3 Medical Conditions During the Natural History Study

In addition to conditions meeting the reporting requirements for an adverse event or as described above, the following medical conditions should also be reported: (1) new diagnosis of a chronic disease (for example, not present at the time of enrollment), and (2) any medical condition that could affect the participant’s ability to carry out any aspect of the protocol or could affect an outcome assessment. These will be reported as adverse events. See chapter 7 for more detail.

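### The adverse event definition is tied to study procedures, which is too narrow for AE data meant as historical controls and conflicts with other sections; a secondary point is that events unresolved at an unrelated death are coded as resolved

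*Protocol*

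**What the plan says.** The adverse event section applies to the Natural History Study phase. Section 7.2.1 limits an AE to an untoward medical occurrence "associated with study procedures whether the event is considered related". Section 7.2.2 then sets the scope of reporting by that definition: "For this protocol, a reportable adverse event includes all events meeting the definition of an" adverse event. It also gives the reason for collecting them: "The purpose of AE collection for the Uni-Rare study will be to provide historical controls for" future clinical trials.

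Other places use a wider scope:

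- **7.2.1, serious adverse events:** "Any untoward medical occurrence that results in any of the following outcomes", with no link to procedures.
- **7.2.3, relatedness:** the reasons for answering No include "and/or the adverse event has no plausible temporal relationship to study procedure".
- **5.3.3, Vision Cohort 3:** at the phone contacts in months 12, 24 and 36, "Changes in medications and AEs will also be collected". The schedule lists no ocular procedure at those contacts.
- **8.3, pregnancy:** an adverse event arising from a pregnancy goes on the adverse event form.
- **8.1.3, medical conditions:** beyond what already meets the AE requirements, newly diagnosed chronic disease and any condition that could affect protocol conduct or an outcome assessment are added: "These will be reported as adverse events".

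On outcome coding, 7.2.7 says that events "ongoing at the time of death; however, were not the cause of death, will be recorded" as resolved at the time of death. Its ongoing category repeats the rule and makes the date of death the stop date. For a participant lost to follow-up whose outcome cannot be determined, 7.2.7 keeps the last known outcome.

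**The concern.** A control rate is useful only if it counts the same kinds of events as the trial it is compared with. For background adverse events, that means events of any cause, with relatedness recorded as a separate attribute. Section 7.2.1 makes association with a study procedure part of the definition itself. A site that follows it literally would leave out a background event that falls in none of the added groups, and an event never entered may not be recoverable later.

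The protocol gives this weight. Section 1.5 lists common AE definitions across sites among its measures against bias, and section 10.3 names adverse events, with eligibility, as the site data most important to monitor. With approximately 40 sites and the determination left to each investigator, sites that read the definition differently would collect different things under one heading.

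The death rule is a smaller matter of the same kind. An event that had not resolved is given a label that means recovery.

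**Working it through.** No arithmetic applies, because the protocol gives no event rate, death rate or sample size for this point. The check is a comparison of sections.

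**Step 1: which rule governs capture.** Section 7.2.2 ties reportability to the AE definition, so the wording of 7.2.1 decides what is entered, apart from explicit additions elsewhere.

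**Step 2: is the restriction only a slip?** The final clause of 7.2.1 reads as if the words *or not* had dropped out after *whether*. Restoring them makes relatedness irrelevant to the definition, but the phrase tying the event to study procedures remains.

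**Step 3: is the wording consistent with the rest?** It is not.

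- A serious event with no tie to a procedure meets the SAE definition but not the AE definition that governs reporting. The serious category is thus wider than the category it should sit within.
- Section 7.2.3 classifies AEs that have no plausible link in time to a procedure. Such events can hardly be associated with one.
- Section 5.3.3 asks for AEs in years when Vision Cohort 3 has no procedures.
- Section 8.3 expects AEs caused by pregnancy.

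**Step 4: what remains outside.** The examples are illustrations, except the corneal abrasion, which section 1.4.1 lists as a risk.

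- Corneal abrasion from a pressure measurement: inside 7.2.1.
- New diabetes: outside 7.2.1, but brought in by 8.1.3.
- An ocular inflammation that could affect a visual field test: brought in by 8.1.3.
- Hospital admission for an unrelated acute illness: an SAE by 7.2.1, but its reportability under 7.2.2 is unclear.
- A short febrile illness between visits, with no bearing on any test: outside both 7.2.1 and 8.1.3.

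Section 8.1.3 presents its items as additional to conditions that already qualify as AEs. If an AE already meant any untoward occurrence, most of that addition would be redundant. A site can therefore reasonably read 7.2.1 narrowly.

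**Step 5: direction of the effect.** Let P be the rate of procedure-associated events, C the rate of further events captured through 8.1.3 or another explicit rule, and A the rate of everything else. The literal rule yields P + C where the full background rate is P + C + A. The captured share is (P + C)/(P + C + A), which is below 1 whenever A is above 0. The protocol gives none of P, C or A, so the shortfall has a sign but no size.

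**Step 6: the death rule.** Both resolved categories in 7.2.7 describe recovery, without or with sequelae. An event still ongoing at an unrelated death fits neither. The same unresolved event keeps its last known outcome if the participant is lost to follow-up, but becomes resolved if the participant dies. This raises the proportion resolved. The stop date is the date of death, which is also the correct end of observation, so the recorded interval is unchanged and only the outcome label is wrong.

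**The case against.** The best defence is that the narrow reading is not how the protocol is meant to work. The SAE definition, the unrelated category, the phone collection, the pregnancy rule and 8.1.3 all point to broad capture, so 7.2.1 may simply be badly worded. As evidence of intent this stands. It does not settle the matter, because 7.2.2 makes the definition operative and the procedure link survives the obvious correction of the grammar. Case report forms or training material might resolve the ambiguity, but they are not available here.

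Three stronger readings are tempting, and the protocol does not support them:

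- *Vision Cohort 3 could have no qualifying event for almost the whole four years.* This uses 7.2.1 alone. Under 8.1.3, a new chronic disease or a condition that could affect an outcome assessment in those years is reported as an AE.
- *The AE data would consist mainly of reactions to diagnostic tests.* The 8.1.3 additions and the unlinked SAE definition rule out that inference.
- *The death rule distorts event duration.* The date of death is the stop date under the rule and under the proposed correction alike.

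On the death rule, it can also be said that the not-resolved category calls for site follow-up, which is impossible after death, and that the event causing death is coded fatal and so remains identifiable. This explains the convention, and few records may be involved. It does not make resolved a true description of the outcome.

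**Conclusion.** The point holds as a conflict between the AE definition and both its stated purpose and several other sections. On the literal text, acute events that are unrelated to procedures and have no bearing on protocol conduct or outcomes are not captured, so the background AE rate would be too low. This assumes that at least some sites apply the definition as written and that such events occur. How far it would make a future treatment look less safe depends also on whether that trial counts all events, which the protocol cannot tell us. The size cannot be derived.

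The outcome coding at an unrelated death is a secondary point. It overstates resolution and is inconsistent with the rule for loss to follow-up, again by an amount that cannot be sized.

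Adverse events are not part of the NHS Objectives 1-3 analyses in chapter 9, so no main estimate of the study changes. The damage is confined to the historical-control use that 7.2.2 names. The change should be made, because it concerns data collection at sites and an analysis plan cannot repair it afterwards.

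**What to change.** In 7.2.1, define an adverse event as any untoward medical occurrence from NHS enrollment to study end, whether or not it is associated with or related to a study procedure. Record relatedness separately, as 7.2.3 already provides. Align 7.2.2 with this definition, and reword 8.1.3 so that its items read as examples within the definition.

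In 7.2.7, record an event ongoing at a death it did not cause as not resolved at death, with the date of death as the end of observation. State that no further site follow-up is needed in that case.

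The cost is protocol wording, eCRF wording and guidance, and somewhat more AE entries at sites. No analysis for NHS Objectives 1-3 changes.
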